3.10.5.3 BRIEF-P scores

The BRIEF-P is a questionnaire entered for subjects ≥ 2 to < 5 years of age to assess subjects' executive functioning. The questionnaire comprises 63 questions with entry options of N (never; scored as 1 point), S (sometimes; scored as 2 points), and O (often; scored as 3 points). Higher scores reflect poorer functioning. The questions are categorized in 5 components: Inhibit, Shift, Emotional Control, Working Memory and Plan/Organize. Additionally, three subscales will be used to calculate subscale scores.

The BRIEF-P form should be used for subjects ≥ 2 to < 5 years of age, with the following exception: for subjects who completed the BRIEF-P at Baseline assessment and turns 5 years of age between that assessment and the initial YEV, the BRIEF-P should be completed through and including initial YEV, and subsequently the BRIEF should be completed. Moreover, if a subject was below 2 years of age at Baseline but turns ≥ 2 years between Baseline and initial YEV, BRIEF-P will be assessed at visits after initial YEV.

Table 3–11 presents which questions belonging to which component and the constitution of subscales.

Table 3–11: BRIEF-P components and subscales

Scale/Index	Questions
Inhibit	3, 8, 13, 18, 23, 28, 33, 38, 43, 48, 52, 54, 56, 58, 60, 62
Shift	5, 10, 15, 20, 25, 30, 35, 40, 45, 50
Emotional Control	1, 6, 11, 16, 21, 26, 31, 36, 41, 46
Working Memory	2, 7, 12, 17, 22, 27, 32, 37, 42, 47, 51, 53, 55, 57, 59, 61, 63
Plan/Organize	4, 9, 14, 19, 24, 29, 34, 39, 44, 49
ISCI	All questions from Inhibit and Emotional Control
FI	All questions from Shift and Emotional Control
EMI	All questions from Working Memory and Plan/Organize
GEC Score	1-63

EMI=Emergent Metacognition Index, FI=Flexibility Index, GEC=Global Executive Composite, ISCI=Inhibitory Self Control Index

Standardized T-scores are determined from each subject's raw GEC, ISCI, FI, EMI, and component scores based on the subject's age and sex. Tables that map each raw score to the

appropriate T-score are provided in the BRIEF-P Professional Manual and will be reproduced programmatically.

Similar to analysis for BRIEF, the T-scores for BRIEF-P will be categorized using the legacy and the dichotomous approach to summarize categorical shift from Baseline. The same categorization as described in Section 3.10.5.2 applies.

Two validity scales will also be derived: Negativity to assess the extent to which the respondent answers selected BRIEF-P items in an unusually negative manner and Inconsistency to assess the extent to which the respondent answers similar BRIEF-P items in an inconsistent manner. The Negativity scale is the number of items in 30, 44, 46, 47, 53, 55, 56, 57, 59 and 63 with a score of 3, and so has a range of 0 to 10. A score of 2 or less is considered acceptable, 3 as elevated and 4 or more highly elevated.

For the Inconsistency scale, there are 10 item pairs of related questions. The Inconsistency scale is the sum of the absolute values of the difference in scores for the items in each item pair, and so ranges from 0 to 20. The item pairs are questions 1 and 11, 3 and 33, 5 and 45, 10 and 20, 11 and 26, 16 and 21, 18 and 52, 33 and 38, 43 and 52, and 48 and 54. A score of 7 or less is acceptable and 8 or more inconsistent.

BRIEF-P will be conducted at ScrV, EV (for DE and LTFU subjects respectively), at FEVs, YEVs and FV/EDV.

Change from Baseline in BRIEF-P scores (raw scores and T-scores) will be calculated as:

$$\begin{aligned} \text{Change from Baseline in BRIEF - P} \\ = \text{BRIEF - P score at postBaseline visit} - \text{BRIEF - P score at Baseline} \end{aligned}$$

at each visit in the Evaluation Period, if Baseline value is available for all BRIEF-P scores (the 5 scales, 3 Indices and GEC scores). A change from Baseline < 0 indicates improvement and a change from Baseline > 0 worsening.

3.10.5.4 PedsQL

The PedsQL is a validated instrument that consists of generic core scales suitable for use with pediatric populations, including those with acute or chronic health conditions (Varni et al, 1999). The PedsQL Measurement Model consists of developmentally appropriate forms for pediatric subjects ≥ 2 years to ≤ 4 years, ≥ 5 years to ≤ 7 years, ≥ 8 years to ≤ 12 years, and ≥ 13 years to ≤ 18 years of age. PedsQL generic core scores will be calculated for each of the following 4 PedsQL scales for subjects ≥ 2 years of age using most recent pre-dose data:

- Physical functioning
- Emotional functioning
- Social functioning
- School functioning

The underlying item score values 0 to 4 (representing responses of: never, almost never, sometimes, often and almost always) will be transformed by the function: $(100 - [\text{response} \times 25])$ in order to generate scores of 0, 25, 50, 75 and 100 where a higher value represents a better HRQoL.

Each dimension score is then calculated as the mean of the transformed item scores from items of the considered dimension. In the case of item-level missing data, these will be replaced by the average of non-missing item scores from the considered dimension, if at least 50% of the items from that dimension are non-missing.

Summary scores will also be generated:

- the Psychosocial Health Summary Score will be calculated as the mean of items (transformed scores after replacement of missing data) from the Emotional, Social, and School Functioning dimensions. However, in the case where the Emotional, Social, or the School Functioning scores would be missing, the Psychosocial Health summary score will be set to missing.
- the Physical Health Summary score (same as Physical functioning dimension).
- the Total score will be calculated as the mean of all PedsQL items (transformed scores after replacement of missing data). However, in the case where one of the dimension scores (Physical, Emotional, Social, or School Functioning) would be missing, the Total score will be set to missing.

PedsQL will be conducted at ScrV, EV (for DE and LTFU subjects respectively), at FEVs, YEVs and FV/EDV. The version of the PedsQL appropriate for each subject's age should be completed, with the following exception: If a subject ages up to the next version of the PedsQL between the Baseline assessment and the initial YEV, the version that was used at the Baseline assessment should be completed through and including the initial YEV, and subsequently the version consistent with his/her age at the time of assessment should be completed.

Change from Baseline in PedsQL score will be calculated as:

$$\begin{aligned} \text{Change from Baseline in PedsQL} \\ &= \text{PedsQL score at postBaseline visit} - \text{PedsQL score at Baseline} \end{aligned}$$

if Baseline value is available. A change from Baseline > 0 indicates improvement and a change from Baseline < 0 worsening.

3.11 Changes to protocol-defined analyses

There are no changes to analyses specified in the protocol.

4 STATISTICAL/ANALYTICAL ISSUES

4.1 Adjustments for covariates

No statistical testing is planned; therefore, this section is not applicable.

4.2 Handling of dropouts or missing data

The method for handling missing and partial data for medications and AEs is described in Section 3.10.4.1 and Section 3.2.3.1 respectively. Missing AE intensity or relationship will be imputed according to worst case scenario with severe intensity and assumed to be related. For other safety variables, no imputation methods are planned.

Regarding efficacy variables, endpoints using seizure frequency and seizure free days based on DRC data will be calculated over non-missing diary days during each study period or time interval as described in Section 3.10.3.1; days for which seizure diary data were not obtained will not be considered in the calculation of seizure frequency or seizure days. This is applicable to the analysis taking all seizure categories into account as well as to the analysis taking only POS seizures into account. Generally, compliance with the daily seizure diary is expected to be high in a refractory population and, therefore, the impact of missing diary data is expected to be minimal. Because the evaluation of efficacy is not the primary objective of this study, and because this is an uncontrolled study in a variable setting, which allows individualized optimization of dosing of BRV and concomitant AEDs, no summaries assessing the impact of missing seizure diary days are planned.

For subjects who prematurely discontinue during the Up-Titration, Evaluation or Down-Titration Period, the calculation of seizure frequency, seizure free days and seizure freedom will be based on available seizure diary days while the subject was receiving BRV. This effectively imputes the unobserved seizure frequency after discontinuation with the seizure frequency observed prior to discontinuation. The presence of such dropouts may influence the evaluation of the long-term outcomes for subjects who either do not discontinue or do not discontinue early in the study. Therefore, as described below, selected summaries will be produced by exposure duration cohorts to allow an assessment of long-term outcomes without the potentially confounding influence of earlier discontinuations.

Endpoints using seizure data from EEG will only include available data. No imputation method will be conducted.

4.3 Interim analyses and data monitoring

Due to the single-arm open-label design of this study, no formal interim analysis as such will be performed. However, data may be reported prior to the completion of this study to support ongoing data cleaning, annual reports, regulatory submissions, and publications.

For regulatory submissions based on interim cutoffs, overall summaries will consider all assessments after the first dose of BRV and prior to or on the date of the clinical cutoff for subjects who are ongoing at the time of the clinical cutoff.

4.4 Multicenter studies

Efficacy and safety outcomes will not be assessed for individual investigator sites due to the expected low number for enrollment within each investigator site.

4.5 Multiple comparisons/multiplicity

No statistical testing is planned; therefore, this section is not applicable.

4.6 Use of an efficacy subset of subjects

All subjects who receive at least 1 dose of BRV and have at least 1 post-Baseline DRC or EEG will be included in efficacy summaries. No additional efficacy subsets are defined for this study.

4.7 Active-control studies intended to show equivalence

This section is not applicable for this study.

4.8 Examination of subgroups

Selected summaries will be provided for the following subgroups as specified within each of the following sections:

- Previous pediatric BRV study experience, labelled with “Cohort” (LTFU subjects overall and by core study, DE subjects)
- Age group (≥ 1 month to < 2 years of age (28 days to 23 months), ≥ 2 to < 4 years of age, ≥ 4 to < 12 years of age, ≥ 12 to < 17 years of age)
- Seizure category (POS, PGS*, Typical Absence, PGS) as defined in Section 3.10.3.
- Geographical region (North America, Latin America, Western Europe, Eastern Europe, Asia/Pacific/Other)

5 STUDY POPULATION CHARACTERISTICS

5.1 Subject disposition

An overall summary of disposition will be provided for enrolled subjects, in SS and FAS, and in SS by subgroups, separately. The following will be summarized:

- The number of enrolled subjects
- The number of screen failures (DE subjects only)
- The number of subjects in the SS (applicable for enrolled subjects table only)
- The number of subjects excluded from the SS (applicable for enrolled subjects table only)
- The number of subjects in the FAS (applicable for enrolled subjects table only)
- The number of subjects entering the Up-Titration, Evaluation, Down-Titration Period
- The number of subjects completing the Up-Titration and entering the Evaluation
- The number of subjects completing the study
- The number of subjects ongoing in the study (only applicable before final data base lock)
- The overall number of subjects discontinuing and the number of subjects discontinuing by primary reason for discontinuation. If the subject discontinued the study and the termination CRF is not available, the reason for discontinuation will be reported as “UNKNOWN”.

Overall subject disposition will also be summarized by cohort (LTFU vs. DE), and geographical region, by seizure category and by core study for the SS.

The number of subjects by cohort and geographical region will be summarized for the SS.

The number of subjects in each analysis set (Enrolled Subjects, SS and FAS) will be presented by investigator and cohort, including the dates of the first subject in (date of earliest EV for the N01266 study) and the last subject out (date of final scheduled or UV). The table will be presented overall and by region.

The number of subjects and Kaplan-Meier estimates of the percentage of subjects completing 3, 6, 12, 24, 36, 48 and 60 months of treatment with BRV in the N01266 study will be provided.

This analysis will be based on duration of exposure to BRV as defined in Section 3.2.7. Subjects who have permanently discontinued will be analyzed as events on the final day of treatment with BRV; subjects who complete the study will be censored on the final day of treatment with BRV.

Subjects who transferred sites will be summarized according to their original site.

Subject disposition will be listed for all subjects enrolled and will include the following information: subject status (screen failure, completed or discontinued), date of informed consent, date and time of first and last study medication (including relative day for last dose), date of premature study termination (if applicable) and primary reason for termination (if applicable) and date of last contact. For screen failures the date and reason for screen failure will be listed.

5.2 Protocol deviations

Important protocol deviations are deviations from the protocol, which potentially could have a meaningful impact on either the primary efficacy outcome or key safety outcomes for an individual subject. The criteria for identifying important protocol deviations and the classification of important protocol deviations will be defined within the project Data Cleaning Plan. Important protocol deviations will be reviewed as part of the ongoing data cleaning meetings prior to database lock to confirm exclusion from analysis sets.

The number and percentage of subjects with at least 1 important protocol deviation will be summarized in SS overall and by category of protocol deviation. This summary will be presented overall, by age group, by seizure category and by cohort (see Section 4.8).

All important protocol deviations will be provided in a data listing.

6 DEMOGRAPHICS AND OTHER BASELINE CHARACTERISTICS

Demographic and other Baseline characteristic variables will be presented for the SS and will be summarized by age group as categorized in Section 4.8, and overall.

Unless otherwise mentioned, for DE subjects, demographic and Baseline variables will be obtained at ScrV, whereas for LTFU subjects, all demographic and Baseline variables will be based on data collected at the time of entry into the core study.

6.1 Demographics and Baseline characteristics

Baseline age will be determined at either ScrV (DE subjects) or EV (LTFU subjects). Age will be calculated based on an assumed date of birth of January 1 for subjects who only have a year of birth based on region-specific regulations.

Body Mass Index will be calculated as:

$$\text{BMI} = \frac{\text{weight in kilograms}}{(\text{height in meters})^2}$$

The age will be calculated as:

- years= (intck('month',brthdtc,rficdtc)-(day(rficdtc) < min(day(brthdtc), day(intnx('month', rficdtc, 1)-1))) /12

- months = intck('month', birth, somedate) - (day(somedate) < day(birth));

Age (in years), age (in months), gender, overall racial group (White, Black, Asian, Other), racial group (American Indian/Alaskan Native, Asian, Black, Native Hawaiian or Other Pacific Islander, White, Other/Mixed), ethnicity (Hispanic or Latino, not Hispanic or Latino), region (North America, Latin America, Western Europe, Eastern Europe, Asia Pacific and others), weight (kg), height (cm), BMI (kg/m^2), BMI category (< 18.5 , 18.5 to < 25 , 25 to < 30 , ≥ 30 kg/m^2), head circumference (cm) and seizure category at ScrV (POS, PGS*, typical absence seizures, PGS, UNC) will be summarized. This summary will be repeated by cohort, by seizure category, by core study and by geographical region.

All demographic and Baseline characteristics will be listed.

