9 EFFICACY ANALYSES

All presentation for efficacy parameters will be based on the FAS and will be summarized by age group (<2 years and ≥ 2 years of age) and seizure category as categorized in Section 4.8, and overall.

Efficacy variables will be assessed using the seizure count information recorded on the DRC and EEG data. Endpoints derived from the DRC will be summarized separately from those derived from the EEG. EEG data collected from 24-hour EEG and 1-hour EEG will be presented separately.

Details of the derivations for all efficacy variables are provided in Section 3.10.3.1.

All summaries of efficacy data are descriptive; no statistical testing will be performed.

All seizure data and derived endpoints will be listed. Data from Up-Titration Period (DE subjects only) and Down-Titration Period will be listed only, if not otherwise mentioned.

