9.1 Seizure based variables based on EEG data

EEG summaries will be presented by age group (< 2 years (24 hour EEG), ≥ 2 years (1 hour EEG)) and by seizure category. Outputs will explicitly restrict the analyses on 24 hour EEG to subjects < 2 years of age. If we have 1 hour EEG assessments for subjects categorized as < 2 years of age according to the Baseline age, we will perform sensitivity analyses in which we present results only by age group (< 2 years, ≥ 2 years), irrespective of the type of EEG performed. The POS and PGS* results for subjects ≥ 2 years will be missing, because EEG is only performed for subjects within Typical Absence seizure category there.

All analyses will be based on data assessed in Evaluation Period only.

Absolute and percent change in ADF will be summarized by age group and seizure category. Additionally, absolute and percent change in POS ADF will be summarized similarly.

Number of responders based on all seizure categories and the corresponding responder rate will be presented. Same will be presented for response based on POS only.

The number and percentage of seizure free subjects (Seizure freedom) will be presented.

Absolute and percent worsening based on PGS seizure types will be summarized.

All raw EEG seizure counts and derived efficacy variables will be listed.

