12.3 PCST Criteria for Vital Signs

Parameter (Unit)	Age Range	Abnormality criteria
Pulse Rate (beats/minute)	<6m	<100 >180
	$\geq 6m - < 3y$	<90 >150
	$\geq 3y - < 12y$	<60 >130

Parameter (Unit)	Age Range	Abnormality criteria
	$\geq 12y - < 17y$	<50 >120
Systolic Blood Pressure (mmHg)	<6m	<60 >100
	$\geq 6m - < 3y$	<70 >120
	$\geq 3y - < 12y$	<80 >140
	$\geq 12y - < 17y$	<90 >160
Diastolic Blood Pressure (mmHg)	<6m	<40 >65
	$\geq 6m - < 3y$	<45 >75
	$\geq 3y - < 12y$	<50 >80
	$\geq 12y - < 17y$	<50 >105
Body Weight	1m - <17y	<3% or >97% of the normal body weight growth curve ranges based on gender and the age of subject on date of weight assessment
	$\geq 17y$	A decrease/increase from Baseline of $\geq 10\%$

m=month, y=year.

Note: A month is defined as 30 days; a year is defined as 365.25 days.

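### Imputing 1 January for birth-year-only subjects overstates age by 6 months on average, which puts infants in older laboratory and vital-sign bands and moves some children aged 1 or 3 years up an age group

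*SAP*

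**What the plan says.** SAP section 6.1 gives the rule: "Age will be calculated based on an assumed date of birth of January 1 for subjects who only have a year of birth". The sentence goes on to limit it to regions whose regulations withhold the full date. The age formulas in the same section count completed months from the birth date.

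Age is then used in several places:

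- **Age groups (section 4.8).** The youngest group is glossed as "28 days to 23 months". The others are "≥ 2 to < 4 years of age, ≥ 4 to < 12 years of age, ≥ 12 to < 17 years of age". Section 8 splits all safety summaries by these groups.
- **Efficacy (section 9).** Results "will be summarized by age group (<2 years and ≥ 2 years of age) and seizure category".
- **EEG (section 9.1).** "Outputs will explicitly restrict the analyses on 24 hour EEG to subjects < 2 years of age". For subjects of 2 years or more, the section expects no POS or PGS* EEG results.
- **PCST limits (Appendices 12.1 and 12.3).** Many limits change at 6 months and at 1, 2 or 3 years. Body weight is judged against growth centiles by sex and "the age of subject on date of weight assessment".
- **Questionnaires (sections 3.10.5.1 to 3.10.5.3).** T-scores depend on age and sex.

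The SAP has no correction, no fallback to a recorded age and no sensitivity analysis for subjects with an imputed birth date.

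**The concern.** 1 January is the extreme of the possible dates, so the error has one sign. An overstatement of several months matters little for a 10-year-old. This study enrols from 1 month of age, where the same error can exceed the child's whole age and cross one or more limits.

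Three things are at stake. An infant can be judged against laboratory, pulse and blood pressure limits meant for older children, and can look light for age on the growth curves. A child truly under 2 with a 24-hour EEG can be classed as 2 or older and so drop out of the output that carries the secondary EEG variables for that age. Safety columns by age group can include children who belong in the column below. Because missing birth dates follow regional rules, and region is itself a subgroup, any such errors would cluster by region.

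**Working it through.** The SAP states no figure for this effect, so there is none to reproduce.

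**Inputs.** Birth date set to 1 January (section 6.1). Group widths from section 4.8: 1 month to <2 years, 23 months; 2 to <4 years, 24; 4 to <12 years, 96; 12 to <17 years, 60. Assumptions, not in the SAP: true birthdays even over the year, and true ages even within each group.

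**Size of the error.** Error = computed age − true age = time from 1 January to the true birthday, even on 0 to 12 months. Mean = 12/2 = 6 months; minimum 0; maximum just under 12 in exact time. It is zero only for a true 1 January birth.

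**Who can cross a limit.** A child t months below a group's upper limit crosses if the error is at least t, with probability 1 − t/12 for t up to 12 and 0 beyond. A child truly under 12 months is more than 12 months from the 2-year limit and cannot cross it. The same holds at 4 years for a child of 24 to <36 months.

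**Share moved up.** Integrating 1 − t/12 over t from 0 to 12 gives 6, so the share is 6 / group width:

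| True age group | Share of affected subjects moved up |
|---|---|
| 1 month to <2 years | 6/23 = 26.1% |
| 2 to <4 years | 6/24 = 25.0% |
| 4 to <12 years | 6/96 = 6.3% |
| 12 to <17 years | 6/60 = 10.0%, computed as 17 or older, outside every listed group |

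Simulated calendar dates with the SAP's completed-months formula give 26.2% and 24.9% for the first two rows.

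**Dependence on the age mix.** The share is 0% if all affected children are in the lower year of the group (under 12 months, or 24 to <36) and 50% if they are spread evenly over the upper year (12 to <24, or 36 to <48). A linear tilt to the young end gives 8 to 9%; to the old end, 42 to 43%. A tight cluster near a limit goes higher: 75% if all are 18 to <24 months.

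**PCST example.** Born in mid-December, seen in late February: true age 2 months. Counted from 1 January of the birth year, 12 months to the next 1 January plus 1 completed month = 13 months. In Appendix 12.1 the GGT limit moves from >522 (under 6 months) past >279 (6 months to <1 year) to >66 U/L (1 year and over); 522/66 = 7.9-fold lower. In Appendix 12.3 the upper pulse limit moves from >180 to >150, so a pulse of 160 would be flagged.

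**Mid-year date for comparison.** The error is then even on −6 to +6 months, with mean 0. The share moved up is 1.5 / width, where 1.5 is the integral of (6 − t)/12 over t from 0 to 6. Under 2 years: 1.5/23 = 6.5% up, against 26.1%. For 2 to <4 years: 1.5/24 = 6.25% up and 6.25% down, 12.5% in all, against 25.0% all upward.

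**The case against.** A reader might infer that infants leave the under-2 group, or that a quarter of all infants and toddlers are misplaced. Neither is supported. Children under 12 months always stay under 24 months after imputation; for them the harm is confined to bands and norms within the group. The 26% and 25% apply only to subjects with an imputed birth date, and only under even age mixes.

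The affected number may be small. The rule applies only where regulations withhold the date. Directly enrolled subjects are at least 4 years old, so misplacement at the 2-year cut, and upward misplacement at the 4-year cut, concerns LTFU children only. The SAP gives no enrolment by age or count of birth-year-only subjects. This stands, and it prevents any statement about the effect on a given table.

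The consequences are also bounded. All summaries are descriptive, efficacy is exploratory, and the primary adverse event counts over all ages are untouched. This stands too.

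Section 9.1 does plan results by age group irrespective of EEG type. Its trigger, though, is a 1-hour EEG in a subject classed as under 2, which is the opposite mismatch. It would not by itself catch a child with a 24-hour EEG who is classed as 2 or older.

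Finally, section 6.1 sits under demographics, and the SAP does not say outright that the imputed date feeds the PCST bands, centiles and T-scores. That is an assumption here. The SAP names no other date, and its months formula takes any date as its end point.

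**Conclusion.** The rule is one-directional and uncorrected. It overstates age by 6 months on average and just under 12 at most, given birthdays even over the year. Infants can be assessed against PCST limits for older children, provided the imputed date is used there. Among affected children, 26% of under-2s and 25% of 2 to <4 year-olds move up a group if true ages are even within the group; the share is 0% or 50% if they fall only in the lower or evenly in the upper year, and more if they cluster just below a limit. Children moved past 2 years leave the 24-hour EEG output, and about 10% of affected 12 to <17 year-olds fall outside every listed group. The study-wide effect cannot be sized without the number of affected subjects. The point justifies a small change to the derivation; it does not call the overall safety results into question.

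**What to change.** In section 6.1, replace the 1 January rule in this order:

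1. Where the core-study or N01266 database holds age in months at entry, use it.
2. Otherwise impute the midpoint of the birth dates compatible with the birth year and the entry age limits at consent: at least 1 month for LTFU subjects, at least 4 and under 17 years for directly enrolled subjects.
3. State that the same date serves age groups, PCST bands, weight centiles and T-scores, and report how many subjects have an imputed date, by age group and region.

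A bare 1 July should not be used. It gives a negative age to a child seen before July of the birth year, and it can put an eligible directly enrolled 4-year-old below 4.

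The cost is one line in the SAP and in the age derivation. Some subjects change age group, and a few children truly aged 2 or older would be classed as under 2. The midpoint removes most of the bias but does not recover the true age: the December infant above would compute as about 7 months (1 July to late February), still one GGT band too old. Recorded age is therefore the first choice.
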